4.3. Exclusion criteria

- Pregnant woman or woman wishing to become pregnant
- Breastfeeding woman
- Patient with an acute exacerbation of allergic rhinitis
- Patient with uncontrolled asthma
- Immunotherapy received within the last two years
- Patient with a known lactose intolerance
- Patient who participated in a clinical study in the previous three months
- Patient who is not sufficiently motivated to engage on a follow-up period of 6 months or more, unable to complete the patient diary, or likely to travel or to move before the end of the study,
- Patient taking nasal or bronchial inhaled corticosteroids on a long term basis (intermittent consumption during the season is permitted provided it is mentioned in the patient's records)

5. Study drugs and concomitant medications

5.1. Description of the study drugs and manufacturing process

The composition of 2LALERG[®] and placebo are described in the table below:

	2LALERG [®]	PLACEBO
Impregnated	Interleukin 1: 17 CH	No impregnation
solution:	Interleukin 4: 17–27 CH	
	Interleukin 5: 17 CH	
	Interleukin 6: 17 CH	
	Interleukin 10: 17 CH	
	Interleukin 12: 9 CH	
	Interleukin 13: 17 CH	
	Tumor Necrosis Factor Alpha: 17 CH	
	Transforming Growth Factor Beta: 5 CH	
	Pulmo histaminum: 15 CH	
	SNA-HLA-II: 18 CH	
Excipients :	Lactose saccharose globules	Lactose saccharose globules
	(380mg/capsule)	(380mg/capsule)
Primary	Red capsules (color degradation ranging	Red capsules (color degradation
packaging :	form dark red to pink, 5 colors)	ranging form dark red to pink, 5
		colors)
Secundary	Aluminium sealed blister of 10 capsules	Aluminium sealed blister of 10
packaging :	numbered from 1 to 10,	capsules numbered from 1 to 10,
	Labelled 2LALERG-PLACEBO 10A16-	Labelled 2LALERG-PLACEBO
	15A16	10A16-15A16
Final packaging :	Printed cardboard box (see annex 1)	Printed cardboard box (see annex 1)
	containing 3 blisters and one leaflet	containing 3 blisters and one leaflet
	explaining how to take the medicine (see	explaining how to take the medicine
	annex 2)	(see annex 2)

The manufacturing process consists of 4 steps:

STEP 1: DILUTION PREPARATIONS

STEP 2: IMPREGNATION

STEP 3: GLOBULES ENCAPSULATION: PRIMARY PACKAGING

STEP 4: SECUNDARY PACKAGING and FINISHED PRODUCT PACKAGING

The placebo is manufactured exactly as the 2LALERG[®], except that it contains only the neutral globules without the homeopathic dilutions impregnated on it. The capsulation, blisterisation and final packaging process are exactly identical for both.

[figure not shown]
5.2. Administration of study drugs

Treatment used: 2L[®]ALERG - Placebo Pharmaceutical form: Capsules - doses containing impregnated granules Excipients: Lactose, Sucrose (granules) to a capsule.

Dosage: 1 capsule daily, fasting morning, following the numerical order of 1 to 10 capsules. When capsule 10 has been taken, start the next blister at capsule 1.

Administration mode:

Open the capsule, pour the contents (granules) under the tongue and let it dissolve. The pellets will be taken on an empty stomach, 15-30 minutes before the morning meal, or one hour after the meal if forgotten.

1. Open carefully the capsule maintaining the capsule's head upward

2. Pour the content (granules) under the tongue and allow melting

Contraindications: None

Warnings and precautions:

This medicine contains lactose. Lactose intolerance cases have been described. The amount of lactose present in the capsules is theoretically sufficient to trigger symptoms of intolerance. In cases of outbreaks of diarrhoea, the patient should consult his/her doctor. As with any homeopathic medicine, it is advisable to avoid taking mint or its derivatives and stimulant products (coffee, chocolate) during one hour before the intake.

Adverse reactions (frequency and seriousness)

Exceptionally, it may appear dyspepsia when taken during fasting. In this case, the granules will be taken one hour after the meal.

Difficulties falling asleep can occur when taken after 16 hours.

As with all homeopathic treatment, worsening of symptoms printing can occur, which usually disappears after a few days. If this impression persists, a physician should be contacted.

Dosage adjustment: Not applicable

5.3.Permitted and prohibited drugs and treatments

Allowed treatments:

- Already established treatments for associated pathologies not liable to have an impact on the proper conduct of the study,
- Rescue medication allowed in the first-line adjuvant treatment is: oral or topical antihistamines (nasal or eye) and eye cromoglycate, topical nasal corticosteroids (in case of failure or insufficiency of those above).

Not allowed treatments:

- Oral or injectable corticosteroids
- Anti-leukotrienes

5.4. Randomization and blinding

The randomization list will be prepared by a Data Manager (independent from the clinical team involved in the study) from the Data Management Department of the CRO, using the randomization module of nQuery Advisor (Version 7.0), ensuring a ratio 1:1 between the study drug and the placebo in each centre.

The investigator of each centre will assign treatment in an ascending order to his/her patients.

The study will be double-blind, meaning that nor the investigator, nor the patient will know the treatment group (active or placebo) to which the patient belongs. The study drug and the placebo will have exactly the same aspect, form, odour and colour. Their packaging will also be exactly the same.

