Study Title	Randomized, double-blind, placebo-controlled study to measure 2L [®] ALERG (homeopathic drug) efficacy on symptoms of allergic rhinitis and allergic rhinoconjunctivitis in patients with a seasonal allergy to grass pollen
Study Acronym	LLB-2016-01
EudraCT number	2016-000097-38

1. Medical Advisor

[name] [name], Pneumo-allergologie, [name], Belgium

2. Principal Investigator

[name], ResearchLink sprl, [name], Belgium

3. Project Manager (Sponsor)

[name], Ind. Pharm.

4. Project Manager of the Contract Research Organization (CRO)

[name], BSc., ECSOR, [name], Belgium

5. Medical writing (Sponsor)

[name], BSc., Labo'Life France

6. Medical Writing, Data Management and Biostatistics (CRO)

[name]

7. Clinical Monitoring (CRO)

[name], Graduated Nurse

8. Pharmacovigilance (CRO)

[name], Semaphar, [name], Belgium

SYNOPSIS

Study Title	Randomized double-blind, placebo-controlled study to measure 2L [®] ALERG (homeopathic drug) efficacy on symptoms of allergic rhinitis and allergic rhinoconjunctivitis in patients with seasonal allergy to grass pollen
Objectives	Primary objective: To demonstrate the superiority of 2L [®] ALERG over placebo in terms of efficacy on the symptoms of allergic rhinitis and allergic rhinoconjunctivitis in patients with seasonal allergy to grass pollen, corrected according to rescue medication intake
	Secondary objectives: To compare the allergy symptoms, the rescue medication intake, the quality of life and the safety in patients treated with 2L [®] ALERG or with a placebo
Study design	Multicentre, randomized, double-blind, two-parallel group, interventional placebo-controlled study Phase IV - notified homeopathic medication, marketed since 2002
Number of centres planned	•
Study Therapy	20 General Practitioners (GPs)
	Micro-Immunotherapy medication
Planning study	Total study duration: maximum 9 months Recruitment period: 1 month Duration of patient treatment: 6 months Duration of patient follow-up : up to 8 months
Patient Population	50 patients per group to achieve 40 cases completed per group, i.e., a total of 100 patients included for 80 cases completed.
Duration of Study Follow-	Screening before the peak of pollination

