Study cohorts	 Two cohorts will be defined: Intention-to-treat (ITT) cohort including all patients having been exposed to at least one dose of the investigational product and in whom at least one efficacy or safety information has been collected after V0. Per protocol (PP) cohort including of the ITT having strictly adhered to the protocol and having a compliance between 80% and 120%. The primary cohort for the statistical analyses will be the ITT cohort. The patients who will prematurely stop the study will not be replaced.
Statistical analysis	A Statistical Analysis Plan (SAP) will be written by the Biostatistician of the CRO in charge of the study. This document will constitute the reference document as far as statistical analyses and statistical methodologies are concerned. It will be approved and signed by the Sponsor and the Principal Investigator before the last patient last visit at the latest. The objective will be to demonstrate the superiority of 2L [®] ALERG over placebo. This will be demonstrated using an independent Student's test comparing the over-time T5SS (corrected with RM) evolution (AUCs) of the two study groups, over the whole treatment period. A P value lower than 5% will be considered statistically significant.

ABBREVIATIONS

AE	Adverse Event
AFMPS	Agence Féderale des Médicaments et des Produits de Santé
AUC	Area Under the Curve
CD	Cluster Differentiation
СН	Centésimale Hahnemannienne
CRA	Clinical Research Associate
CRF	Case Report Form
CRO	Clinical Research Organization
GCP	Good Clinical Practice
GM-SF	Granulocyte-Macrophage-Stimulating Factor
HLA	Human Leukocyte Antigen
ICF	Inform Consent Form
ICH	International Conference on Harmonization
IgE	Immunoglobulin E
IL	Interleukin
ITT	Intention-To-Treat
MedDRA	Medical Dictionary for Regulatory Activities
PP	Per Protocol
RM	Rescue mediation
SAE	Serious Adverse Event
SAP	Statistical Analysis Plan
SAR	Serious Adverse Reaction
SmPC	Summary of Product Characteristics
SNA	Specific Nucleic Acid
SUSAR	Suspected Unexpected Serious Adverse Reaction
T5 SS	Total 5 Symptoms Score
Th	T helper
TNF	Tumour Necrosis Factor

Table of Contents

1.	BACKGROUND AND STUDY RATIONALE	9
1.1.	BACKGROUND	9
1.2.	STUDY RATIONALE	9
1.3.	BENEFITS AND RISKS FOR PEOPLE INVOLVED IN THE STUDY	14
1.4.	DESCRIPTION AND JUSTIFICATION OF THE THERAPEUTIC SCHEMA	14
2.	OBJECTIVES AND ENDPOINTS	15
2.1.	PRIMARY OBJECTIVE AND PRIMARY ENDPOINT	15
2.2.	SECONDARY OBJECTIVES AND SECONDARY ENDPOINTS	15
3.	STUDY DESIGN	16

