2.1. Primary objective and primary endpoint

The main objective is to demonstrate the efficacy of 2L[®]ALERG versus placebo on the symptoms of allergic rhinitis and allergic rhino-conjunctivitis in patients with seasonal allergy to grass pollen.

The primary endpoint will be the area under the curve (AUC) of the overall score established according to the total 5 symptoms score (T5SS) and medication score (MS) according to time from the start of treatment until the end of the patient follow-up.

The five symptoms (sneezing, rhinorrhoea, nasal pruritus, eye itching and tearing, and nasal obstruction) will be assessed daily by patients on a scale from 0 (no symptoms) to 3 (severe symptoms) giving a total score ranging from 0 to 15.

The rescue medications (RM) allowed in the first-line adjuvant treatment will be codified to establish a score.

The allowed RM are the oral antihistamines (two points per day of use) or local treatment (nasal or eye; a point per day), and the ocular cromoglycate (one point per day).

In case of failure or in case of insufficiency of rescue medications mentioned above, the nasal topical corticosteroids (one point per day of use) will be allowed.

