7.1. Data collection and handling of study data

Data collection

Data collection will be done on paper CRF for each patient,

The patient will fill in the patient diary card given by the investigator and bring it back at the next visit. The investigator will check the patient diary card and will keep it in the patient CRF The sponsor will be responsible for the printing of CRFs (NCR carbon paper) and patient diaries, which will be sent to each investigator.

The persons allowed to fill in the CRF are identified in the delegation of responsibilities sheet witch is to be kept in the Trial Master File.

Data coding

By signing this protocol the investigator and all the staff are committed to keep confidential the identities of the patients participating in the study.

Each patient will be identified by a numerical code consisting of 4 digits: YY/ZZ (YY corresponding to the centre number and ZZ to the patient number).

A form will be made available to the investigator so he could note the correspondence between the numeric code and the patient's identity. He/she must keep this document in his/her Trial Master File.

Collection Data Processing

The compilation of clinical data will be based on the structuration of a clinical database (IBM SPSS Data Entry Builder) and the creation of input screens in the image of CRF and diary card in accordance with the Protocol and the legislation currently in force.

This database will be validated and documented appropriately.

All data will undergo a double data entry process in the database, by two independent encoders, using the IBM SPSS Data Entry Interviewer software.

Based on the regular cleaning of data, queries will be generated to the investigational centres. The answers to these queries will also be encoded in the database.

7.2.Biostatistics

Sample size calculation and justification

The objective of the study will be to show the superiority of 2L[®]ALERG over placebo in the treatment of patients suffering from seasonal allergy to grass pollen.

For the sample size calculations two references have been used. The first is a study conducted with 2[®]LALERG versus placebo in patients with a pollen allergy. ^[1]

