The second is a more theoretical publication from Clark and Schall (2007) supporting the recommendations made in a World Allergy Organization document on methodological aspects of immunotherapy trials. The average of the Average Rhinoconjunctivitis Total Symptom Score (ARTSS) and Average Rescue Medication Score (ARMS) should be considered as a primary efficacy variable in clinical trials of immunotherapy for allergic rhinoconjunctivitis. ^[35]

Version 1.0, 04 February 2016, Page 25

The global score calculated in the paper of [name] et al. (2011)^[1], taking into account the T5SS total score and the RMS total score, fits very well with the recommendation from Clark and Schall (2007)^[35].

The Figure 5 of [name] et al.'s paper has been used to evaluate the area under the curve (AUC) of global score for the placebo and 2L[®]ALERG groups. ^[1]

[figure not shown]

Fig. 5. Comptages polliniques et évolution du score global (moyenne et écart-type) dans les groupes actif et placebo pendant la période d'étude.

The values were approximately 80 for the placebo group and 55 for the treated group (a reduction of about 30% with the active treatment. These values have been used to build several sample size scenarios.

Scenario	1	2	3	4	5
Test significance level, α	0.050	0.050	0.050	0.050	0.050
1 or 2 sided test?	2	2	2	2	2
Group Placebo mean, μ1	80.000	80.000	80.000	80.000	80.000
Group 2L [®] ALERG mean, μ ₂	55.000	55.000	55.000	55.000	55.000
Difference in means, μ1 - μ2	25.000	25.000	25.000	25.000	25.000
Common standard deviation, σ	20.000	25.000	30.000	35.000	40.000
Effect size, $\delta = \mu_1 - \mu_2 / \sigma$	1.250	1.000	0.833	0.714	0.625
Power(%)	90	90	90	90	90
n per group	15	23	32	43	55
Total N completed patients	30	46	64	86	110

A sample size of 32 patients in each group will have 90% power to detect a difference in means of 25 (the difference between a placebo group mean, μ_1 , of 80 and a 2L[®]ALERG group mean, μ_2 , of 55) assuming that the common standard deviation is 30 using a two group t-test with a 0.05 two-sided significance level.

With a sample size of 43 patients in each group, the same assumptions are valid with a common standard deviation of 35.

The final recommendation will be to include 50 patients per group in order to achieve at least 40 evaluable patients per group taking into account a potential drop-out rate of 20%.

Statistical analyses

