A Statistical Analysis Plan (SAP) will be written by the Biostatistician of the CRO in charge of the study. This document will constitute the reference document as far as statistical analyses and statistical methodologies are concerned. It will be approved and signed by the Sponsor and the Principal Investigator before the last patient last visit at the latest.

Study cohorts

Two cohorts will be defined:

- Intention-to-treat (ITT) cohort including all patients having been exposed to at least one dose of the investigational product and in whom at least one efficacy or safety information has been collected after V0.
- Per protocol (PP) cohort including of the ITT having strictly adhered to the protocol and having a compliance between 80% and 120%.

The primary cohort for the statistical analyses will be the ITT cohort.

The patients who will prematurely stop the study will not be replaced.

Statistical methods

The IBM SPSS Statistics (Version 21.0 and eventual upgrades) software will be used throughout statistical analyses.

Missing values will not be replaced, nor extrapolated.

Classical descriptive statistics will be used to describe the patient population at baseline.

The two groups will be compared at baseline using independent Student's t tests for continuous variables and Mann-Whitney's tests, Chi-square tests or Fisher's exact tests for discrete variables.

The superiority of the active treatment over placebo will be demonstrated using an independent Student's test comparing the over-time T5SS (corrected with RM) evolution (AUCs) of the two study groups over the whole treatment period. A P value lower than 5% will be considered statistically significant.

The comparisons between the two study groups in terms of secondary endpoints will be done using the appropriate statistical methods, as they will be described in the SAP. No correction being applied for the multiplicity of endpoints, p values lower than 5% will be considered with caution, as indicative only of potential statistically significant differences between the two groups for the secondary endpoints.

8. Pharmacovigilance and management of adverse events

8.1.Definitions

Adverse events

An adverse event is defined as any untoward medical occurrence in a patient or a participant in a clinical trial, whether or not considered drug related.

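### Randomisation is balanced within about 20 GP centres, but the fixed primary t-test has no centre term: valid, yet mildly conservative if centres differ

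*Protocol*

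**What the plan says.** - **Allocation.** Section 5.4 describes a list "ensuring a ratio 1:1 between the study drug and the placebo in each centre". The synopsis plans 20 GP centres. Centre is therefore a factor on which the design balances. No block size is given.
- **Primary test.** The synopsis says of superiority: "This will be demonstrated using an independent Student's test comparing the over-time T5SS (corrected with RM) evolution (AUCs) of the two study groups". Section 7.2 (Statistical methods) repeats it: "The superiority of the active treatment over placebo will be demonstrated using an independent" Student's test on the AUCs. Neither place mentions centre. Section 7.2 leaves the methods for the secondary endpoints to the SAP, but names the primary test itself.
- **Sample size.** Section 7.2 uses a two-group t-test, two-sided 5%, difference 25 (80 versus 55). It gives 32 per group at SD 30 and adds: "With a sample size of 43 patients in each group, the same assumptions are valid with a common standard deviation of 35". It recruits 50 per group to have at least 40 evaluable after 20% drop-out.
- **Centre identifier.** Section 7.1 builds each patient code as two pairs of digits, "YY corresponding to the centre number and ZZ to the patient number".
- **Endpoint.** Under section 2.1 the symptoms are self-rated by patients every day, so no centre rater is involved.

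**The concern.** The analysis does not follow the groups within which the trial randomises. With equal numbers of active and placebo patients in a centre, a high or low centre level adds equally to both arms and cancels from the difference in means. The t-test's pooled SD still contains that centre variation. Its standard error is then larger than the real sampling error, its p-value is too cautious and its confidence interval too wide.

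What is at stake is precision only. About 40 evaluable patients per group are expected, or about 4 per centre (80/20). At SD 35 that is three per group short of the 43 which the protocol's own table requires for 90% power. Precision that costs no patients is therefore of some use.

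**Working it through.** **1. The plan's own figures.** The smallest n with at least 90% power from the noncentral t distribution (difference 25, two-sided 5%) is 15 / 23 / 32 / 43 / 55 at SD 20 / 25 / 30 / 35 / 40. This matches the table in section 7.2 exactly. Drop-out: 40/(1 − 0.20) = 50, also as stated.

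**2. Power at the expected n.** At SD 35 and 40 per group, the noncentrality is (25/35)·√(40/2) = 3.19 on 78 df, and power is 88.4%. At 41, 42 and 43 per group it is 89.2%, 89.9% and 90.6%. At SD 30 and 40 per group it is 95.7%.

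**3. Why the t-test is conservative: the fully balanced case.** Take K = 20 centres with 2 + 2 evaluable patients each, so n = 40 per group. Let ICC be the share of AUC variance lying between centres, and set total variance to 1.
- Variance that actually enters the treatment contrast: 1 − ICC.
- Expected pooled variance in the t-test: (1 − ICC) + ICC·2(K − 1)/(n − 1) = (1 − ICC) + ICC·38/39.
- Ratio of true to estimated SE: r = √[(1 − ICC) / ((1 − ICC) + ICC·38/39)].
- At ICC 0.10: r = √(0.900/0.9974) = 0.950. The actual type I error is about 2·P(T₇₈ > t₀.₉₇₅/r) = 3.9%.
- At ICC 0.02 / 0.05 / 0.20 / 0.30 the same formula gives 4.8 / 4.5 / 2.9 / 2.0%.

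**4. More realistic layouts.** Drop-out and odd-sized centres spoil exact balance and soften the effect. The simulation had 40,000 runs per setting, 100 patients in 20 centres, 20% random drop-out, normal AUC and a difference of 25. There were three layouts: 5 per centre in blocks of 4; unequal centres (1 to about 20 patients) in blocks of 4; and 5 per centre in blocks of 2. Ranges run over the layouts. ICC, block size and centre sizes are assumptions, because the protocol states none of them.

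| Assumed ICC | 0 | 0.05 | 0.10 | 0.20 |
|---|---|---|---|---|
| t-test: type I error, % | 4.8–5.1 | 4.6–4.9 | 4.4 | 3.6–3.7 |
| t-test: mean SE ÷ true SD of estimate | 1.00 | 1.01 | 1.03 | 1.07 |
| Random centre (Kenward-Roger): type I error, % | 5.1–5.3 | 5.1–5.4 | 5.1–5.2 | 4.9–5.1 |
| t-test: power at SD 35, % | 87.8–88.3 | 88.5–88.8 | 88.9–89.2 | 89.7–90.0 |
| Random centre: power at SD 35, % | 88.0–88.5 | 89.2–89.6 | 90.2–90.5 | 92.6–92.9 |
| Raw gain at SD 35, points | 0.2 | 0.7 | 1.3–1.5 | 2.9–3.0 |
| Gain at exactly 5% error, SD 35, points | −0.3 to 0.1 | 0.1–0.6 | 1.2 | 2.8–3.0 |
| Gain at exactly 5% error, SD 30, points | −0.1 to 0.1 | 0.1–0.3 | 0.5–0.6 | 1.2–1.3 |
| Centre variance estimated as zero, % of trials | 53–55 | 33 | 19 | 5–6 |
| 20 fixed centre effects versus t-test, SD 35, points | −4.1 to −3.8 | −3.1 to −2.3 | −1.5 to −1.0 | +1.1 to +1.5 |

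The rows at exactly 5% error rescale the mixed model's critical value so that its type I error is 5% in that setting, then compare its power with the t-test as planned. On that footing the 95% CI is 0.6% narrower to 0.4% wider at ICC 0, and narrower by 0.4–1.7% at 0.05, 2.8–3.3% at 0.10 and 7.5–8.1% at 0.20. With Satterthwaite df the type I error was 5.1–5.5% throughout. Monte Carlo error is about 0.11 points for type I error, 0.16 for power and 0.2–0.3 for the recalibrated gains.

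**5. Translation into patients.** At SD 35 and ICC 0.10: 88.4% + 1.2 = 89.6%, which lies between the t-test's power at 41 (89.2%) and 42 (89.9%) per group. The gain is worth one to two evaluable patients per group.

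**The case against.** The case for leaving the plan alone is a fair one.

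- **Nothing is invalid.** The t-test holds 5% or less within simulation error, and sample size and analysis use the same test. This stands in full. The point is about efficiency.
- **The ICC is unknown and may be small.** The endpoint is built from patients' own daily ratings. This stands, and it is why the gain can only be given as a range.
- **SD 35 is the favourable case.** At SD 30 power is already 95.7% with 40 per group, and the gain at ICC 0.10 is 0.5–0.6 points. The ITT cohort may also keep drop-outs who have diary data. With up to 50 per group, t-test power would be as high as 94.3% (SD 35) or 98.5% (SD 30). Both facts reduce what can be recovered.
- **The mixed model is not exact.** Its type I error can run to about 5.4% (Kenward-Roger) or 5.5% (Satterthwaite). The recalibrated gains are only a benchmark, since a real analysis cannot recalibrate. This is a real, small cost.
- **The SAP is the reference document for methods and could add a centre-adjusted analysis.** That is possible. But the protocol does not leave the primary test open: it names an unadjusted one twice, and the two documents would have to agree.

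These points limit the size of the finding. They do not remove the mismatch between how patients are allocated and how the primary comparison is made.

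**Conclusion.** The point holds as an optional improvement. The design balances on centre and the primary test ignores centre. The consequence is a test that is exact if centres do not differ and mildly conservative if they do, never one that favours the product. In the three layouts with drop-out, the simulated type I error is 4.4% at ICC 0.10 and 3.6–3.7% at 0.20. At SD 35 a random centre intercept held to 5% error gains 1.2 points of power at ICC 0.10 and 2.8–3.0 at 0.20. Below 0.10 the gain is essentially nil. These sizes rest on assumed ICC, block size and centre sizes, and on random drop-out and normally distributed AUC. The direction of the effect does not depend on the particular values chosen.

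**What to change.** In the synopsis and section 7.2, and in the SAP to match:

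1. Define the primary comparison of AUC as a linear model with treatment as a fixed effect and centre as a random intercept, fitted by REML.
2. Name the small-sample correction (Kenward-Roger, or Satterthwaite) and confirm that the release used offers it. Section 7.2 states: "The IBM SPSS Statistics (Version 21.0 and eventual upgrades) software will be used throughout" the analyses.
3. State that the model reduces to the one without centre if the centre variance is estimated as zero.
4. Report the adjusted difference with its 95% CI, and keep the unadjusted t-test as a sensitivity analysis.
5. Do not fit 20 fixed centre effects with about 4 evaluable patients each. In the simulations this lost power at every ICC up to 0.10.

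The cost is wording only, since the centre number is already part of every patient code. The downsides are a slightly more complex model and a type I error that may sit marginally above 5%. If centres do not differ, the model falls back to the t-test in just over half of trials and brings no real gain.
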